3.0 STUDY OBJECTIVES, ENDPOINTS, AND ESTIMANDS

Objectives	Endpoints	Estimands
Primary		
To compare the efficacy of multiple doses of DC-806 versus placebo in adult participants with moderate to severe plaque psoriasis	Proportion of participants achieving PASI-75 at Week 12	Estimand 1a: This estimand is intended to provide a population-level estimate of the anti-psoriatic effect of DC-806 versus placebo on a binary composite responder endpoint (PASI-75) at Week 12 without the benefit of other background anti-psoriasis therapy, regardless of the use of topical bland moisturizers, emollients, or bland shampoos as needed, and regardless of treatment interruption Target Population: Participants with moderate to severe plaque psoriasis • Treatment Conditions: Each of 4 dosing regimens of DC-806 (CCI) compared to placebo administered orally 4 tablets each morning and 4 tablets each evening for 12 weeks irrespective of interruptions and on top of use of topical bland moisturizers, emollients, or bland shampoos as needed • Variable: Responder is defined as achieving ≥75% reduction in PASI-75 at Week 12 without the use of other background anti-psoriasis therapy. Non-responder is defined as not achieving PASI-75 at Week 12 or receiving any prohibited medication ^a (including an alternative therapy for psoriasis and interacting drugs), or discontinuing the treatment due to related AE or requirement for prohibited medication ^a (Composite strategy). • Strategies for Intercurrent Events: As though no discontinuations of treatment due to any other reasons occur (Hypothetical strategy) • Population-Level Summary: Difference in the response rates at Week 12 Estimand 1b: As above but with odds ratio as population-level summary

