		Estimand 8b: As above but with absolute change in BSA score from baseline as Variable			

Confidential Page 31 of 91

Objectives	Endpoints	Estimands
To assess the PK of	Measurement of	N/A
DC-806 and	plasma concentration	
intersubject	of DC-806 at scheduled	
variability in adult	timepoints	
participants with		
moderate to severe		
plaque psoriasis		
Exploratory		
To assess the	Time to PASI-75	N/A
efficacy of DC-806	response at Week 12	
on additional	Proportion of	
efficacy endpoints	participants achieving	
in adult participants	BSA ≤1% psoriasis	
with moderate to	involvement at Week	
severe plaque	12	
psoriasis		
To assess	Change from Baseline	N/A
improvement by	in DLQI at all	
DC-806 in quality-	scheduled timepoints	
of-life assessments		
in adult participants		
with moderate to		
severe plaque		
psoriasis		
To assess	Change from	N/A
improvement by	Baseline in Itch NRS	
DC-806 in psoriasis	at all scheduled	
symptoms in adult	timepoints	
participants with	Change from	
moderate to severe	Baseline in Skin Pain	
plaque psoriasis	NRS at all scheduled	
	timepoints	

Confidential Page 32 of 91

Objectives	Endpoints	Estimands
To assess the PD of	 Measurement of 	N/A
DC-806 in adult	serum biomarkers at	
participants with	scheduled timepoints	
moderate to severe	 Assessment of 	
plaque psoriasis	histologic biomarkers	
	from tissue biopsies	
	of psoriatic skin	
	plaques collected at	
	scheduled timepoints	
	Measurement of gene	
	expression level of	
	key regulators of IL-	
	17 and related	
	pathways	
To assess exposure-	Analyses to explore	N/A
response	relations between DC-	
relationships of	806 exposures and	
DC-806	efficacy endpoints/PD	
	biomarker responses	

AE = adverse event; BID = twice daily; BSA = body surface area; DLQI = Dermatology Life Quality Index; E1a = Estimand 1a; IL-17 = interleukin-17; N/A = not applicable; NRS = numerical rating scale; PASI-XX = XX% reduction in Psoriasis Area of Severity Index score; PD = pharmacodynamic; PK = pharmacokinetics; QD = once daily; SAE = serious adverse event; sPGA = static Physician's Global Assessment; TEAE = treatment-emergent adverse event

Confidential Page 33 of 91

a. Prohibited medications are the medications used for treating psoriasis and also having an impact on the efficacy assessment, and are a subset of the medications listed in Section 6.7.1.

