#### 2.1. Primary Objectives, Endpoints, and Estimands

The primary objectives, corresponding endpoints and estimands are displayed in the below table:

Primary Objectives	Endpoints	Estimands
Primary Objectives To compare the efficacy of multiple doses of DC-806 versus placebo in adult participants with moderate to severe plaque psoriasis	Endpoints Proportion of participants achieving Psoriasis Area of Severity Index score (PASI-75) at Week 12	Estimands Estimand 1a: This estimand is intended to provide a population-level estimate of the anti- psoriatic effect of DC-806 versus Placebo on a binary composite responder endpoint (PASI-75) at Week 12 without the benefit of other background anti-psoriasis therapy, regardless of the use of topical bland moisturizers, or emollients, or bland shampoos, as needed, and regardless of treatment interruption Target Population: Participants with moderate to severe plaque psoriasis Treatment Conditions: Each of 4 dosing regimens of DC-806 (CCI ) compared to placebo administered orally 4 tablets each morning and 4 tablets each evening for 12 weeks irrespective of interruptions, and on top
		
 
morning and 4 tablets each evening for 12 weeks irrespective of interruptions, and on top of use of topical bland moisturizers. or emollients, or bland shampoos, as needed
 
Variable: Responder is defined as achieving ≥75% reduction in Psoriasis Area of Severity Index score (PASI-75) at Week 12 without the use of other background antipsoriasis therapy. Non-responder is defined as not achieving PASI-75 at Week 12 or receiving any prohibited medication* (including an alternative therapy for psoriasis and interacting drugs), or discontinuing the treatment due to related AE or requirement for prohibited medication*. (Composite strategy)
 
Strategies for Intercurrent Events: As though no discontinuations of treatment due to any other reasons occur. (Hypothetical strategy)
 
Population-Level Summary: Difference in the response rates at Week 12
 
Estimand 1b: As above but with odds ratio as population-level summary
 

To compare the safety and tolerability	Incidence proportion of	Estimand 2a: This estimand is intended to provide a population-level estimate of the
of multiple doses of DC-806 versus	treatment-emergent	incidence proportion of treatment-emergent adverse events (TEAEs)
placebo in adult participants with	adverse events (TEAEs),	

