moderate to severe plaque psoriasis	SAEs, and	Target Population: Participants with moderate to severe plaque psoriasis.
	TEAEs leading to	Treatment Conditions: Each of 4 dosing regimens of DC-806 (CCI
	discontinuation	) compared to placebo administered orally 4 tablets each
		morning and 4 tablets each evening for 12 weeks irrespective of interruptions, and on top
		of use of topical bland moisturizers, or emollients, or bland shampoos, as needed
		Variable: Occurrence of TEAEs
		Strategies for Intercurrent Events: While at-risk strategy will be used where the period
		considered is defined up to the end of the follow up
		Population-Level Summary: AE incidence proportion (proportion of participants with
		TEAE)
		Estimand 2b: As above but with SAE as variable
		Estimand 2c: As above but with TEAEs leading to permanent treatment discontinuation
		as variable
		Estimand 2b: As above but with SAE as variable. Estimand 2c: As above but with TEAEs leading to permanent treatment discontinuation as variable.

\* Prohibited medications are the medications used for treating psoriasis and also having an impact on the efficacy assessment, and are a subset of the medications listed in Protocol Section Error! Reference source not found.

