		reason and as though no intake of prohibited medications*. (Hypothetical strategy). All data
		post ICE will be set to missing
		Population-Level Summary: Difference in means
		Estimand 7b: as above but for absolute change in PASI score from baseline as variable.
To compare the efficacy of multiple	Change and percent	Estimand 8a: This estimand is intended to provide a population-level estimate of the anti-
doses of DC-806 versus placebo on	change from Baseline	psoriatic effect of DC-806 on a continuous endpoint (BSA) as though no discontinuations of
additional efficacy endpoints in adult	in the percentage of	treatment for any reason occur, as though no intake of prohibited medications* and
participants with moderate to severe	BSA affected at	regardless of treatment interruption
plaque psoriasis	scheduled timepoints up	
	to Week 12	Target Population: Participants with moderate to severe plaque psoriasis
		Treatment Conditions: Each of 4 dosing regimens of DC-806 (
		) compared to placebo administered orally 4 tablets each morning
		and 4 tablets each evening for 12 weeks irrespective of interruptions, and on top of use of
		topical bland moisturizers, or emollients, or bland shampoos, as needed
		Variable: Change and percentage change from baseline of BSA at scheduled timepoints up
		to Week 12.
		Strategies for Intercurrent Events: As though no discontinuations of treatment due to any
		reason and as though no intake of prohibited medications * . (Hypothetical strategy). All data
		post ICE will be set to missing
		Population-Level Summary: Difference in means
		Estimand 8b: as above but for absolute change in BSA score from baseline as variable

\* Prohibited medications are the medications used for treating psoriasis and also having an impact on the efficacy assessment and are a subset of the medications listed in Section 6.7.1 of the protocol.

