#### 8. Efficacy Analysis

			Main Estin		
	Estimand Description	Analysis Set	Intercurrent Events	Analysis Model/Method	Sensitivity and Supplementary Analyses
Estimand 1a	This estimand is intended to provide a population-level estimate of the anti-psoriatic effect of DC-806 versus Placebo on a binary composite responder endpoint (PASI-75) at Week 12 without the benefit of other background anti- psoriasis therapy regardless of the use of topical bland moisturizers or emollients, or bland shampoos, as needed and regardless of treatment interruption.	FAS	Receiving any prohibited medication* or discontinuing the treatment due to related adverse event or requirement for prohibited medication* → Composite strategy Discontinuing the treatment due to any other reason è Hypothetical strategy Treatment interruption è Treatment policy	Either Fisher's exact or Chi- squared. Participants with no Week 12 data (observed or imputed) will be considered as non-responder.	
Estimand 1b	This estimand is intended to provide a population-level estimate of the anti-psoriatic effect of DC-806 versus Placebo on a binary composite responder endpoint (PASI-75) at Week 12 without the benefit of other background anti- psoriasis therapy regardless of the use of topical bland moisturizers or emollients, or bland shampoos, as needed and regardless of treatment interruption.	FAS	Receiving any prohibited medication* or discontinuing the treatment due to related adverse event or requirement for prohibited medication* → Composite strategy Discontinuing the treatment due to any other reason → Hypothetical strategy Treatment interruption è Treatment policy	
 
Participants with no Week 12 data (observed or imputed) will be considered as non-responder.
 
b) A logistic regression model will be performed with PASI-
 
	

				75 at Week 12 as binary	
				response and treatment,	
				baseline PASI score (as a	
				continuous covariate) as	
				covariates. The following	
				additional covariates will be	
				tested in the model using	
				backward elimination with a	
				significance level of 0.2 to	
				retain the covariates in the	
				model: age, BMI and weight as	
				continuous covariates, sex,	
				previous biologic therapy and	
				geographic region as discrete	
				covariates. At the very least,	
				previous biologic therapy and	
				geographic region will be	
				retained in the model. The	
				conditional odds ratio, with	
				Placebo as reference group,	

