#### 8.1.1. Estimand 1a

#### 8.1.1.1. Main Analysis Approach

A participant receiving any prohibited medication or discontinuing the treatment due to related adverse event or requirement for prohibited medication prior to Week 12 visit will be considered as a non-responder (Composite strategy). If a participant discontinued treatment for reasons other than related adverse event or requirement for prohibited medication, PASI scores after the treatment discontinuation date will be set to missing (Hypothetical strategy). If a participant experienced any treatment interruption, PASI score reported after the treatment interruption will be used as reported (Treatment policy).

Participants without Week 12 PASI score (either due to hypothetical strategy implementation or missed visit) will be considered as non-responder.

A 2-sided, 2-sample Fisher's exact or Chi-squared test will be performed to assess a difference between active treatment groups (DC-806) versus Placebo in PASI-75 at Week 12 for the following comparisons on the FAS:

#### Comparison 1

H0: PASI-75 at Week 12  $_{DC-806\ 800mg}$  = PASI-75 at Week 12  $_{Placebo}$ H1: PASI-75 at Week 12  $_{DC-806\ 800mg} \neq$  PASI-75 at Week 12  $_{Placebo}$ 

#### Comparison 2

H0: PASI-75 at Week 12  $_{DC-806\ 600mg}$  = PASI-75 at Week 12  $_{Placebo}$ H1: PASI-75 at Week 12  $_{DC-806\ 600mg} \neq$  PASI-75 at Week 12  $_{Placebo}$ 

#### Comparison 3

H0: PASI-75 at Week 12  $_{DC-806 400mg}$  = PASI-75 at Week 12  $_{Placebo}$ 

H1: PASI-75 at Week 12  $_{DC-806 \ 400 mg} \neq$  PASI-75 at Week 12  $_{Placebo}$ 

#### Comparison 4

H0: PASI-75 at Week 12  $_{DC-806\ 200mg}$  = PASI-75 at Week 12  $_{Placebo}$ H1: PASI-75 at Week 12  $_{DC-806\ 200mg} \neq$  PASI-75 at Week 12  $_{Placebo}$ 

The number and percentage of participants who are defined as PASI-75 responder will be presented by treatment group. The p-value and unconditional odds ratio with its corresponding 95% CI will be presented in the active treatment group compared to the placebo group. All comparisons will be performed in a prespecified hierarchical procedure starting from the highest dose regimen to the lowest dose regimen.

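### The Estimand 1a non-responder trigger counts interacting drugs in the variable text but only psoriasis drugs in its footnote; separately, the medication start-date rule lacks a guard

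*SAP*

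**What the plan says.** **Responder definition.** In the estimand tables (Protocol 3.0, SAP 2.1), Estimand 1a makes a participant a non-responder for any prohibited medication, "including an alternative therapy for psoriasis and interacting drugs". SAP 2.2 repeats the parenthesis for Estimands 3, 5 and 6.

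The term carries a footnote mark. The protocol footnote reads "Prohibited medications are the medications used for treating psoriasis and also having an impact on the efficacy assessment" and describes these drugs as a subset of the list in Protocol 6.7.1. The footnotes in SAP 2.1 and 2.2 say the same. The SAP Section 8 table states the intercurrent event as "Receiving any prohibited medication* or discontinuing the treatment due to related adverse event or requirement for prohibited medication", without the parenthesis, and its footnote gives the same narrow definition. The estimand's stated aim is an effect "without the benefit of other background anti-psoriasis therapy".

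The analysis text in SAP 8.1.1.1 reads "A participant receiving any prohibited medication or discontinuing the treatment due to related adverse event". It has no footnote mark and no drug list at that place.

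**Date imputation.** SAP 4.1 moves a partial start date that falls in the month or year of first dose to the first-dose date, for adverse events and medications alike. The adverse-event rule then resets a start that lands after the end date to the end date. The medication rule has no such line. SAP 7.1 calls a medication prior only if it both started and stopped before first dose.

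**The concern.** The primary endpoint has two definitions of one of its non-responder triggers. Strong and moderate CYP3A4 inhibitors and strong inducers are on the protocol's prohibited list because of interaction. Apart from cyclosporine, which Protocol 6.7.1 also lists as a psoriasis therapy, they are not among the psoriasis treatments that the protocol names. They count under the variable text and do not count under its footnote.

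The same data could therefore give a responder or a non-responder, depending on which sentence the programmer follows. If this is left open, the choice could be made after data have been seen.

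The date gap is smaller. It can produce a medication record that starts after it stopped, and so misplace a prior drug in the medication tables.

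**Working it through.** **1. The two definitions applied to the same participants**

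| Participant | Variable text | Footnote and Section 8 table |
|---|---|---|
| Takes a psoriasis drug that affects efficacy | Non-responder | Non-responder |
| Takes cyclosporine (in both Protocol 6.7.1 and 10.7) | Non-responder | Non-responder |
| Takes another interacting drug and stops study drug before Week 12 | Non-responder | Non-responder: by the composite rule, or because later scores are set to missing and a missing Week 12 score counts as non-response (SAP 8.1.1.1) |
| Takes another interacting drug, stays on study drug, does not reach PASI-75 | Non-responder | Non-responder |
| Takes another interacting drug, stays on study drug, reaches PASI-75 | **Non-responder** | **Responder** |

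Only the last row differs. Protocol 7.1 lists the need for prohibited medication as a reason to stop study drug, so such a case would mainly be a protocol deviation. It is still possible. Protocol 6.7.2 allows medication judged necessary for the participant's safety, with continuation decided afterwards, and the moderate inhibitors in Protocol 10.7 include ciprofloxacin, erythromycin and fluconazole.

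**2. Size per case**

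Inputs: about 45 per arm (Protocol 9.1, SAP 4.2), and a two-sided Fisher's "exact or Chi-squared test will be performed to assess a difference" (SAP 8.1.1.1). The visible text gives no response rates, so all responder counts below are assumptions, and 0.05 is used only as a yardstick.

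One case moves an arm by 100/45 = 2.2 points.

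With equal arms of 45, a active responders, c placebo responders and R = a + c, the uncorrected chi-squared statistic is 90(a − c)²/[R(90 − R)]. For 13 versus 4: 90 × 81/(17 × 73) = 5.87, p = 0.015. For 12 versus 4: 90 × 64/(16 × 74) = 4.86, p = 0.027. With placebo at 4/45:

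| Active responders | Fisher p | Chi-squared p |
|---|---|---|
| 13 | 0.029 | 0.015 |
| 12 | 0.051 | 0.027 |
| 11 | 0.087 | 0.048 |
| 10 | 0.144 | 0.081 |
| 22 | 0.00005 | 0.00003 |
| 19 | 0.0005 | 0.0003 |

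Losing one case at 13 crosses 0.05 under Fisher but not under chi-squared. Losing one at 11 crosses under chi-squared, where Fisher is already above. Losing three at 22 changes nothing of substance.

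Over a range of assumed placebo counts, one active-arm case crosses 0.05 at a single active count for each test:

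| Placebo responders of 45 | 2 | 3 | 4 | 5 | 6 |
|---|---|---|---|---|---|
| Fisher: active count | 9 | 11 | 13 | 14 | 15 |
| Chi-squared: active count | 8 | 10 | 11 | 13 | 14 |

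A placebo-arm case works the other way. At 13 active responders, moving placebo from 5 to 4 takes Fisher p from 0.063 to 0.029.

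**3. Date rule**

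Illustration: start recorded as 2023 only, stop 20 Apr 2023, first dose 15 May 2023. The year matches that of first dose, so the start is imputed to 15 May 2023, 25 days after the recorded stop (10 days left in April plus 15 in May). The start is not before first dose, so the drug fails the prior definition. With the adverse-event guard the start becomes 20 Apr 2023, and the drug is prior.

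**The case against.** The strongest reply is that the analysis section does settle the matter. SAP 8.1.1.1 sits under a table that states the same trigger without interacting drugs and defines it narrowly, so a missing footnote mark is not a missing definition. Much of this stands. A reader might infer that the SAP leaves the choice wholly open, and the Section 8 table and footnote do not support that. What remains is that the estimand tables in both documents still say the opposite.

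It is also fair that the p-value grid would look the same for any one-participant misclassification, that the counts are assumed, and that Protocol 9.3 calls the analysis descriptive and exploratory. The grid shows only the scale of one case. It does not show how often one occurs.

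On the date rule, a reader might infer three stronger things.

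- **That it reaches the responder flag.** SAP 4.1 limits the imputation to medication, procedure and adverse-event tables, and SAP 2 places intercurrent events after treatment initiation.
- **That the drug would be tabulated as prohibited.** SAP 7.1 states no date test for that table.
- **That the drug must be tabulated as concomitant.** Its recorded stop shows that it was not ongoing at first dose. A program keyed to the imputed start would read it as a new therapy since first dose; one that also checks the stop may place it in neither class.

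**Conclusion.** The inconsistency in the primary responder definition is real and should be corrected. It is a matter of reconciling wording: the footnotes, the Section 8 table and the stated aim all point to the narrow reading. Its reach is one kind of participant, at 2.2 points of one arm per case. With the assumed counts, significance changes only at the margin and depends on the test used.

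A reader might infer that the broad text biases the trial for or against DC-806. The documents do not support a direction, since they give neither the frequency nor the arm of such cases. Nor can it be said that a sensitivity analysis on this point is missing: SAP 8.1.1.2 and 8.1.1.3 are listed in the contents, but their text is not shown.

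The missing date guard is also real. It is minor and confined to the medication tables, and the frequency of partial medication start dates is not given.

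**What to change.** 1. Reconcile the variable text and the footnote to one definition for endpoint derivation in Protocol 3.0 and SAP 2.1 and 2.2. The documents' own signals support the narrow one.
2. Repeat that definition in SAP 8.1.1.1, and freeze the coded list of counted drugs before unblinding.
3. Optionally, analyse the other definition as a sensitivity check if the sections not shown do not already do so.
4. In SAP 4.1, add to the medication rule: if the imputed start is after the end date, imputed or not, set the start equal to the end date.

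The cost is SAP wording, a matching protocol clarification, a coded drug list and one line of derivation code. Steps 1 to 3 concern how the endpoint is derived, not which drugs participants may take.

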#### 2.2. Secondary Objectives, Endpoints, and Estimands

The secondary objectives, corresponding endpoints, and estimands are displayed in the below table:

Secondary Objectives	Endpoints	Estimands
To compare the efficacy of various	Proportion of	Estimand 3a: This estimand is intended to provide a population-level estimate of the anti-
DC-806 dose regimens in adult	participants in each	psoriatic effect of DC-806 (comparison of each dose) on a binary composite responder
participants with moderate to severe	DC-806 treatment	endpoint (PASI-75) at Week 12 without the benefit of other background anti-psoriasis therapy
plaque psoriasis	group achieving PASI-	regardless of the use of topical bland moisturizers or emollients, or bland shampoos, as needed
	75 at Week 12	and regardless of treatment interruption
		Target Population: Participants with moderate to severe plaque psoriasis
		Treatment Conditions: Each of 4 dosing regimens of DC-806 (CC)
		) compared to each of the lower doses administered orally 4 tablets
		each morning and 4 tablets each evening for 12 weeks irrespective of interruptions, and on
		top of use of topical bland moisturizers, or emollients, or bland shampoos, as needed
		Variable: Responder is defined as achieving ≥75% reduction in Psoriasis Area of Severity
		Index score (PASI-75) at Week 12 without the use of other background anti-psoriasis
		therapy. Non-responder is defined as not achieving PASI-75 at Week 12 or receiving any

		
 
prohibited medication* (including an alternative therapy for psoriasis and interacting drugs), or discontinuing the treatment due to related AE or requirement for prohibited medication*. (Composite strategy)
 
Strategies for Intercurrent Events: As though no discontinuations of treatment due to any other reasons occur. (Hypothetical strategy)
 
Population-Level Summary: Difference in the response rates at Week 12
 
Estimand 3b: As above but with odds ratio as population-level summary
 

To compare the efficacy of multiple doses of DC-806 versus placebo on additional efficacy endpoints in adult participants with moderate to severe plaque psoriasis	Proportion of participants achieving an sPGA score of 0 (clear) or 1 (almost clear) with ≥2 grade improvement from Baseline at Week 12	Estimand 4a: This estimand is intended to provide a population-level estimate of the anti- psoriatic effect of DC-806 versus Placebo on a binary composite responder endpoint (sPGA score of 0 [clear] or 1 [almost clear] with $\geq$ 2 grade improvement from Baseline) at Week 12 without the benefit of other background anti-psoriasis therapy regardless of the use of topical bland moisturizers, or emollients, or bland shampoos, as needed and regardless of treatment interruption
		
 
Target Population: Participants with moderate to severe plaque psoriasis.
 
Treatment Conditions: Each of 4 dosing regimens of DC-806 (CCCCCCCCCCCCCCCCCCCCCCCCCCCCCCCCCCCC

To compare the efficacy of multiple doses of DC-806 versus placebo on	Proportion of participants achieving	Estimand 5a: This estimand is intended to provide a population-level estimate of the anti- psoriatic effect of DC-806 versus Placebo on a binary composite responder endpoint (PASI-
additional efficacy endpoints in adult participants with moderate to severe plaque psoriasis	$\geq$ 50%, $\geq$ 75%, $\geq$ 90%, and 100% reduction in PASI score (PASI-50, PASI-75, PASI-90, and	50) at scheduled timepoints without the benefit of other background anti-psoriasis therapy regardless of the use of topical bland moisturizers or emollients, or bland shampoos, as needed and regardless of treatment interruption
	PASI-100,	Target Population: Participants with moderate to severe plaque psoriasis

	respectively) at scheduled timepoints up to Week 12	Treatment Conditions: Each of 4 dosing regimens of DC-806 (CC) ) compared to placebo administered orally 4 tablets each morning and 4 tablets each evening for 12 weeks irrespective of interruptions, and on top of use of topical bland moisturizers, or emollients, or bland shampoos, as needed Variable: Responder is defined as achieving ≥50% reduction in Psoriasis Area of Severity Index score (PASI-50) at scheduled timepoints up to Week 12 without the use of other background anti-psoriasis therapy. Non-responder is defined as not achieving PASI-50 at scheduled timepoints or receiving any prohibited medication* (including an alternative therapy for psoriasis and interacting drugs), or discontinuing the treatment due to related adverse event or requirement for prohibited medication* (Composite strategy) Strategies for Intercurrent Events: As though no discontinuations of treatment due to other reasons occur. (Hypothetical strategy) Population-Level Summary: Odds ratio
		Estimand 5b: As above but with PASI-75 as variable Estimand 5c: As above but with PASI-90 as variable Estimand 5d: As above but with PASI-100 as variable
To compare the efficacy of multiple doses of DC-806 versus placebo or additional efficacy endpoints in adult participants with moderate to severe plaque psoriasis	
 
Proportion of
 
participants achieving
 
an sPGA score of 0 or
 
1 at scheduled
 
Timepoints up to Week 12
 
	Estimand 6: This estimand is intended to provide a population-level estimate of the anti- psoriatic effect of DC-806 versus Placebo on a binary composite responder endpoint (sPGA score of 0 [(clear)] or 1 [almost clear]) at scheduled timepoints without the benefit of other background anti-psoriasis therapy regardless of the use of topical bland moisturizers or emollients, or bland shampoos, as needed and regardless of treatment interruption
		Target Population: Participants with moderate to severe plaque psoriasis. Treatment Conditions: Each of 4 dosing regimens of DC-806 (CCC) ) compared to placebo administered orally 4 tablets each morning and 4 tablets each evening for 12 weeks irrespective of interruptions, and on top of use of topical bland moisturizers, or emollients, or bland shampoos, as needed Variable: Responder is defined as achieving an sPGA score of 0 (clear) or 1 (almost clear) with ≥2 grade improvement from Baseline at scheduled timepoints up to Week 12 without the use of other background anti-psoriasis therapy. Non-responder is defined as not achieving an sPGA score of 0 (clear) or 1 (almost clear) with ≥2 grade improvement from Baseline at scheduled timepoints up to Week 12 or receiving any prohibited medication* (including an alternative therapy for psoriasis and interacting drugs), or discontinuing the treatment due to related adverse event or requirement for prohibited medication* (Composite strategy) Strategies for Intercurrent Events: As though no discontinuations of treatment due to other reasons occur (Hypothetical strategy) Population-Level Summary: Odds ratio

To compare the officerous of multiple	Change and persent	Estimand 7a: This estimand is intended to provide a nonveltion level estimate of the esti-
dosas of DC 806 yerrus pleashe on	change from Pagalina	respiration of DC 806 on a continuous and point (DASI) as though no discontinuations
doses of DC-800 versus placebo on	in DASL soons st	psoriatic effect of DC-800 on a continuous endpoint (PASI) as though no discontinuations
additional efficacy endpoints in adult	in PASI score at	of treatment for any reason occur, as though no intake of prohibited medications * and
participants with moderate to severe	scheduled timepoints up	regardless of treatment interruption
plaque psoriasis	to week 12	
		Target Population: Participants with moderate to severe plaque psoriasis
		Treatment Conditions: Each of 4 dosing regimens of DC-806 (OC)
		) compared to placebo administered orally 4 tablets each morning
		and 4 tablets each evening for 12 weeks irrespective of interruptions, and on top of use of
		topical bland moisturizers, or emollients, or bland shampoos, as needed
		Variable: Change and percentage change from baseline of PASI score at scheduled
		timepoints up to Week 12.
		Strategies for Intercurrent Events: As though no discontinuations of treatment due to any
		reason and as though no intake of prohibited medications*. (Hypothetical strategy). All data
		post ICE will be set to missing
		Population-Level Summary: Difference in means
		Estimand 7b: as above but for absolute change in PASI score from baseline as variable.
To compare the efficacy of multiple	Change and percent	Estimand 8a: This estimand is intended to provide a population-level estimate of the anti-
doses of DC-806 versus placebo on	change from Baseline	psoriatic effect of DC-806 on a continuous endpoint (BSA) as though no discontinuations of
additional efficacy endpoints in adult	in the percentage of	treatment for any reason occur, as though no intake of prohibited medications* and
participants with moderate to severe	BSA affected at	regardless of treatment interruption
plaque psoriasis	scheduled timepoints up	
	to Week 12	Target Population: Participants with moderate to severe plaque psoriasis
		Treatment Conditions: Each of 4 dosing regimens of DC-806 (
		) compared to placebo administered orally 4 tablets each morning
		and 4 tablets each evening for 12 weeks irrespective of interruptions, and on top of use of
		topical bland moisturizers, or emollients, or bland shampoos, as needed
		Variable: Change and percentage change from baseline of BSA at scheduled timepoints up
		to Week 12.
		Strategies for Intercurrent Events: As though no discontinuations of treatment due to any
		reason and as though no intake of prohibited medications * . (Hypothetical strategy). All data
		post ICE will be set to missing
		Population-Level Summary: Difference in means
		Estimand 8b: as above but for absolute change in BSA score from baseline as variable

\* Prohibited medications are the medications used for treating psoriasis and also having an impact on the efficacy assessment and are a subset of the medications listed in Section 6.7.1 of the protocol.

